A number of safeguards will be in place to minimize risk. All interactions with participants will be performed by qualified study personnel. Prior to performing their duties, all study staff who will interact with participants will undergo specific training for their research tasks, with attention being devoted to issues surrounding risk to human subjects. Toward this end, all staff members will be required to complete HIPAA and IRB certification, and will be informed of potential pitfalls relevant to human subject concerns that surround their job duties. Intervention delivery content sent through the automated remote coach will be overseen by the PI who is a licensed occupational therapist and Co-I [name] who is a medical doctor. At the outset of the study and at subsequent three-month intervals, a project staff meeting will be held in which all study personnel will discuss the safety and proper treatment of research participants. These meetings will be mandatory for all project personnel who have contact with participants or with data that result from the study. [name] will be present at these meetings, as well as furnish advice regarding the medical safety of the intervention and how to deal with any medically relevant problems that arise.

Self-report information. Subjects may refrain from answering any questions without prejudice. We also have subjects complete their surveys in our presence when possible. This serves two purposes: 1) we can answer questions that arise regarding individual items, and 2) we can provide immediate assistance if necessary. While severe reactions to answering personal questions are rare; we will offer counseling and emergency resources available to those in need. Participants who complete mailed or digital assessments independently will be provided with a phone number to call with any questions or concerns.

Functional mobility testing. In order to minimize risks associated with functional mobility testing (i.e., the 4-meter gait speed test), participants who attend in-person assessment sessions are instructed to walk a self-selected normal pace. A study team member will be nearby throughout the testing to offer assistance as needed. For those individuals who deem any discomfort or instability too extreme, there is the option of discontinuing the testing procedures.

Physical activity monitoring using accelerometers. We will offer the option of wearing a terry cloth thigh-band underneath the accelerometer if participants are experiencing discomfort from straps or adhesive. The additional layer between the skin and accelerometer eliminates any discomfort associated with the device skin contact and does not affect the data collection process. If this option is not acceptable to the participant, the subject may be excluded from further participation in the study.

Physical activity engagement. To mitigate the risk of engaging in increased levels of physical activity, we have included self-reported screening question that asks individuals if they believe they are safe to regularly walk. Co-I [name]—a medical doctor and geriatrician—has deemed this screening question sufficient given the low-risk and non-prescriptive nature of the intervention. If an individual answers “no” to this question, then he/she will be excluded from the study. Activity engagement during the intervention period is voluntary. We will recommend moderate intensity walking, a low risk physical activity for older adults, during the intervention period (i.e., as part of the goal-setting and remote coaching components of the app). The medical doctor and physical therapist on our investigative team will provide ongoing consultation to ensure safe physical activity engagement. We will ask about adverse events whenever our

team has contact with participants to ensure that we capture all events that may affect data outcomes. If research personnel who have contact with participants become aware of any clinically significant problems related to the health of one of the participants, research personnel will recommend that the participant contact his or her primary care facility and will be available to assist him or her with accessing the necessary services. For emergency events that occur during assessment visits, we will follow standard USC health system protocols.

Exposure to explicit and subliminal positive aging messages. The implicit messages that contain priming words used in the intervention were rated positively in two pilot studies in preparation for a larger study. Therefore, the likelihood that the implicit messages will result in negative views about aging is low. The explicit messages have all been reviewed by the team's social psychologist, [name], who has expertise in older adult stereotype threat. She has confirmed that the messages do not present negative stereotypes that could adversely affect older adults' views on aging. Because the explicit messages may be paired with images of older adults, our team has carefully selected images that reflect a wide range of daily activity capabilities; images reflecting engagement in extraordinary activities (e.g., skydiving) were avoided. The final assessment session, led by a research assistant, will conclude with a careful and detailed debriefing conversation about aging stereotypes and their effects on health and wellness in older adults.

Confidentiality. All information obtained from the participants will be kept confidential among appropriate members of the study group. During computerized data analysis, anonymity of all study participants will be assured by the appearance of their names next to their study IDs only on a single log, to be maintained and stored in a password-protected and HIPAA-compliant REDCap database. Access to the study ID log will only be granted to users that need this information to follow-up with the participant. With respect to study personnel who will interact with participants, we will maintain strict standards that forbid the leakage of information about study participants to unauthorized individuals either within or outside the study team. These strategies are likely to succeed in eliminating any possible harm to participants due to leaking of personal information. A description of mitigating the risks of being audio recorded during the interviews is included in section IV. A.3: Confidentiality. Each of the above safeguards is expected to substantially reduce the participants' study participation risks.

C. Potential Benefits to Human Subjects and Other

All individuals who complete the four-month intervention will have access to specialty features of a physical activity-based smartphone app not yet commercially available. Because the risks are minimal, and because the study promises to generate knowledge about optimizing a smartphone app to encourage physical activity in older individuals, the benefits of the study outweigh the risks. For all participants, it is likely that the opportunity to participate in a potentially successful mobile health intervention for older adults and the knowledge that one is aiding in the quest to develop improved mobile health interventions will benefit the participants to a degree that outweighs the risks.

D. Importance of Knowledge to be Gained

The knowledge that will result from the study is expected to have important benefits for society. Older adults represent the most physically inactive age group, which places them at high risk for chronic, disabling conditions. The proposed PA app suite is a unique mobile health tool that shows promise in improving older adults' PA and overall health. A feasibility study of this app shows that older adults are willing to utilize a PA-tracking app and find it easy to use and potentially beneficial for health. The proposed study will provide valuable information on how to design and develop an acceptable and usable smartphone app intervention with maximal potential to improve physical activity and overall health in the ever-growing population of older adults. This project will also support future development and testing of the PA-tracking app suite compared to alternative mobile health interventions that target elders and thereby contribute to national healthy aging agendas. The cumulative value of this knowledge far outweighs the risks identified in the previous section.

V. References

1. Vogel, T., et al., *Health benefits of physical activity in older patients: A review*. International Journal of Clinical Practice, 2009. **63**(2): p. 303-20.
2. Blake, H., et al., *How effective are physical activity interventions for alleviating depressive symptoms in older people? A systematic review*. Clinical Rehabilitation, 2009. **23**(10): p. 873-887.
3. Sherrington, C., et al., *Exercise to prevent falls in older adults: an updated meta-analysis and best practice recommendations*. New South Wales Public Health Bulletin, 2011. **22**(4): p. 78-83.

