One-hundred community-living older adults who are served by Front Porch Center for Innovation and Wellbeing (FPCIW) will be primarily recruited from FPCIW's 2000-member senior network in Los Angeles. FPCIW will facilitate recruitment, referring its eligible members to the study team. Justification for the targeted sample size is multifold. First, an adequate number of participants will be available to enable meaningful analyses (final N=90) given a four-month attrition rate of 10% (estimate based on averaging interval-adjusted study completion rates in five studies of mHealth or web-based PA interventions for adults aged >40 years[47-52]. Second, the expected overall (N=90) and per-feature (n=45) sample sizes well exceed the number of participants previously described as necessary to determine if a larger trial is warranted.[53] Third, the stipulated sample size is easily achievable and represents roughly the maximum number of participants attainable given available funding resources.

Persons will be deemed eligible based on the following criteria. Inclusion criteria: men or women, 65–84 years old; English speaking; reside in LA or in Pacific Time Zone if participating remotely; score ≥ 5 on a 6-item cognitive screener[54]; report <150 minutes of moderate-to-vigorous PA/week as per a single-item screener;[55] ambulatory; ability to safely participate in PA as determined by self-report of ability to regularly walk safely; smartphone owner for ≥ 1 month; observed ability to reliably access and operate a smartphone during orientation; available by telephone for the duration of either study. Exclusion criteria: unwillingness to meet at local community venues and/or via online meetings to comply with study procedures for the length of each study. Although not an eligibility criterion per se, access to a computer and webcam, and sufficient computer skills to participate in virtual orientation is necessary if in-person orientation is not feasible.

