Study measures (apart from the four-meter walk test and collection of usage data) will be either (1) mailed or dropped off/picked up through contactless hand delivery to participants, including paper-based instructions or a link to video-based instructions and a pre-addressed/postage pre-paid envelope—telephone assistance will be made available to complete requested study tasks; (2) emailed with instructions for electronic completion—telephone assistance will be made available to complete requested study tasks; and/or (3) administered by a condition-blind tester at a FPCIW or other community venue at baseline and/or post-intervention. A combination of remote plus in-person assessment session contact may be deemed necessary based on participant needs. The most likely scenario for this hybrid contact is if participants need in-person support to don their activity monitor appropriately. This will be decided on a case-by-case basis and is unlikely to be necessary for more than a few participants.

In-person sessions will typically include 2–8 participants, with the assessment battery lasting approximately 1.5 hours. *Objective PA level* (primary targeted outcome) and *objective SA time* will be assessed during a three-day monitoring period pre- and post-intervention the activPAL (Pal Technologies Ltd), a thigh-worn monitor that is considered the gold-standard for tracking sedentary behavior in free-living conditions.[56-58] Proprietary algorithms available from activPAL software analysis program will be used to aggregate PA- and SA-related data. (Although the PA-tracking core app provides useful intervention-facilitating PA feedback,[59] app-based PA records will not be used as outcome data because they have not been validated for this purpose and do not include useful baseline information.) Auto-calculated times identified by activPAL software will be used to identify wear periods and sleep/wake times, with participant reports of these periods as manually entered into the device for the purpose of corroboration.

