Self-reported PA will be measured via the Physical Activity Scale for the Elderly (PASE).[60] PASE is a ten-item instrument designed to assess engagement in PAs commonly encountered by older adults, including those related to leisure, household, and occupational tasks. The tool is a valid and reliable measure of PA engagement in older populations.[60, 61] For assessment sessions conducted in-person, *Functional mobility* will be assessed through a four-meter walk test,[62-65] a commonly used, validated measure of physical and functional performance in older adults.

The potential mediators *PA self-efficacy, self-regulation, outcome expectation, and social support* will be measured using the 78-item PA scale of the Health Beliefs Survey.[66, 67] Subscales demonstrate sufficient internal consistencies (Cronbach's $\alpha=0.68-0.90$) and are predictive of PA.[32] *Aging self-perceptions* will be assessed by the Attitudes Toward Own Aging subscale of the Philadelphia Geriatrics Center Morale Scale.[68, 69] This five-question tool captures the subjective aging experience, shows moderate internal consistency (Cronbach's $\alpha=0.61-0.64$), and predicts mortality risk.[27] *Views of aging* will be measured using the Attitudes to Ageing Questionnaire,[70] a 24-item tool that assesses subjective views about age-related psychosocial, physical, and psychological changes; is cross-culturally valid; and is psychometrically sound (Cronbach's $\alpha=0.68-0.84$).[70] *Usage behavior* (e.g., frequency of opening the app) will be captured via the app platform, and *perceived usefulness* of assigned features will be measured via the the Mobile App Rating Scale – Adapted user version [uMARS], as well as the post-study phone interview (included to inform optimization beyond information gleaned from the clinical trial).

Table 1 summarizes the study's measurement plan for Aims 1 and 2. Each of the aforementioned pre-existing assessments has been validated for use with community-dwelling older adults.

Table 1. Overview of Study Variables

| Category | Variable(s) | Primary Role in Study | Measurement | Timing |

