Our biostatistician will secure and archive data, and will oversee all data analytic functions. Usage data for each participant will be obtained from storage within the app and downloaded manually at in-person assessment sessions. Data will be transferred to the biostatistician for analysis and storage on the USC secure network. activPAL data will be downloaded and cleaned. Using proprietary algorithms supplied by PAL Technologies, waking-hour wear periods will be identified for use in analysis.

Data analysis will be organized around the goal of providing multiple sources of information useful for future efforts to optimize the Moving Up app suite. We will calculate *descriptive statistics* at baseline and/or post-intervention for demographic, *app usage behavior* [proportion of days opening the app ≥ 1 time], *user satisfaction* [perceived app quality, physical activity-related (*objective physical activity* [primary outcome; daily steps], *sedentary activity time* [daily sitting time], *self-reported physical activity*, *functional mobility* [gait speed]), and mediational (i.e., *self-efficacy for physical activity*, *self-regulation for physical activity*, *family social support for physical activity*, *outcome expectation for physical activity*, *aging self-perceptions*, *views of aging*) outcome variables, both for the overall sample and by on/off status of each of three specialty features (i.e., Proof Positive, Coach Me, and On Your Feet).

Indicator variables will be created to code whether or not the participant had each of the specialty features installed on their phone as part of the intervention. Results regarding outcomes and hypothesized mediators will be calculated overall and by feature subgroup. The feature subgroups are not mutually exclusive since a participant can be randomized to receive 0, 1, 2, or all 3 of the features.

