Data will be collected from participants by blinded raters at two assessment sessions (pre- and post-intervention) or via US mail, contactless hand delivery/pick-up, or secure email for digital completion, two three-day activity monitoring periods (pre- and post-intervention), and during a four-month intervention period. Data to be gathered at the pre- and post-intervention assessment sessions include demographic and background information, health beliefs regarding physical activity, self-reported physical activity, and sedentary time. If assessment sessions are held in-person, functional mobility will be assessed during a four-meter walk test administered by trained research personnel. Upon completion of assessment sessions, data coding forms and materials will be delivered to the study center at USC and kept in locked file drawers. During each of the three-day activity monitoring periods, participants will wear a research-grade accelerometer. Activity patterns and wear patterns tracked through this device will be manually downloaded to and stored on a secure database. During the four-month intervention period, participants will be utilizing the PA-tracking core app/mechanical pedometer and specified specialty features on their smartphones. Data automatically captured through the app such as activity patterns (e.g., minutes engaged in moderate intensity activity) and app usage behaviors (e.g., frequency of accessing various app features) will be gathered through the in-app tracking software. These data will be downloaded from the app database and transferred to a secure USC server in coded format as described above. Participants will be educated (verbally and via a written SOP ["Information Collected in App"]) when they install the app, about data that will be collected within the app, what will happen to those data at the end of the study. A short interview to collect usability and feasibility data will be conducted during the final phone check-in just after completion of the 4-month intervention. For this study, participant identities will be known to the project manager and authorized personnel except for research staff who will complete blinded evaluations during the pre- and post-intervention assessment sessions.

A.3. Potential Risks

The overall risk to subjects in this study is low.

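### The plan gives two retrieval routes for app usage data; the in-person route, if followed, would leave usage missing for remote participants and for dropouts who attend no final session

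*Combined protocol and SAP*

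**What the plan says.** The retrieval of usage data is described in several places.

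- **Section III (Data Management, Analysis, & Statistical Considerations):** "Usage data for each participant will be obtained from storage within the app and downloaded manually at in-person assessment sessions".
- **Section IV.A.2 (Sources of Materials):** usage behaviours captured automatically by the app "will be gathered through the in-app tracking software", and then "These data will be downloaded from the app database and transferred to a secure USC server in coded format as described above". No visit is mentioned.
- **Section II.C (Procedures & Measurement), on capture:** usage "will be captured via the app platform".
- **Section II.C, on delivery of measures:** the list of mail, email and tester-administered routes opens with an exception: "Study measures (apart from the four-meter walk test and collection of usage data) will be either".

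Remote participation is allowed. Section II.B accepts people who "reside in LA or in Pacific Time Zone if participating remotely" and provides for virtual enrolment and consent. Sections II.C and IV.A.1 let the assessments be done by mail, hand delivery or email, and expect mixed remote and in-person contact for only a few people.

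Table 1 defines objective usage as the proportion of days on which the app is opened, over the full study duration. Section II.A.2 names usage rates among the inputs to component selection, alongside effect sizes and satisfaction ratings. Section III compares usage by feature (assigned or not) with one-tailed t-tests.

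**The concern.** The Section III rule is written for every participant but relies on a visit that some participants will not make. Because usage covers the whole intervention period, only a download at the post-intervention session would give the complete record. A participant assessed by mail or email has no such session, and a dropout may not attend one.

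The plan deliberately gives significance tests on activity outcomes less weight and draws on a wider set of evidence, so usage matters more here than in a conventional trial. App use is also voluntary (Section IV.A.3), so the records of people who stop using it are informative. No section says how usage is retrieved from remote or withdrawn participants, or how missing usage is handled.

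**Working it through.** **Step 1: set the routes side by side.**

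| Source | Where usage comes from | Visit needed? | Remote participants or dropouts addressed? |
|---|---|---|---|
| Section III | storage within the app, manual download | yes, in-person session | no |
| Section IV.A.2 | app database, transferred to server | none mentioned | no |
| Section II.C, capture | app platform | not stated | no |
| Section II.C, delivery of measures | usage excepted from the listed routes | not stated | no |

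The first two rows describe different procedures for the same variable. The last two do not settle which applies.

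**Step 2: reproduce the plan's own figure.** Inputs from Sections II.A.2, II.B and III: 100 randomised, 10% attrition, 45 against 45 per feature, effect size d = .45, alpha .10 one-tailed, 80% power for daily steps.

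- Completers: 100 × (1 − 0.10) = 90, or 45 per level.
- Normal approximation: power = Φ(d·√(m/2) − z₀.₉₀), with m per level. For m = 45: .45 × √22.5 = 2.135, and 2.135 − 1.282 = 0.853, so Φ = 0.803.
- Noncentral t: 0.800. The plan's figure reproduces.

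**Step 3: apply the in-person rule to usage.** The remote share is not stated, so 25%, 50% and 75% of the 90 completers are assumed. The plan states no effect size for usage and does not restate alpha for that test, so .45 and .10 are borrowed from daily steps. With equal levels, the standard error of the feature difference grows by √(90/n).

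| Assumed remote share | Usage n = 90 × (1 − share) | SE multiplier | Power (noncentral t) | d detectable at 80% power |
|---|---|---|---|---|
| 0% | 90 | 1.00 | 80% | 0.45 |
| 25% | 67.5 | 1.15 | 71% | 0.52 |
| 50% | 45 | 1.41 | 58% | 0.63 |
| 75% | 22.5 | 2.00 | 41% | 0.90 |

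The planned attrition of 10 among the 100 randomised comes on top of these losses.

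**Step 4: effect of losing dropouts on mean usage.** If completers average c and the 10% who drop out average w, a completers-only mean exceeds the mean over everyone by c − (0.9c + 0.1w) = 0.1(c − w). Assuming c = 60–70% of days and w = 10–30%, the range is 0.1 × (60 − 30) = 3 to 0.1 × (70 − 10) = 6 percentage points. These opening rates are assumptions; the documents give none.

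**Step 5: with the database route.** If every log is retrieved, the comparison can use up to 50 against 50: .45 × √25 − 1.282 = 0.968, so Φ = 0.83 on the same borrowed inputs.

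**The case against.** The strongest reply is that a workable route is already written. Section IV.A.2, in a paragraph that also covers mail, hand delivery and email, has usage gathered automatically and downloaded from an app database. Section III does not say that an in-person session is the only means of retrieval. A reader might infer that the data will certainly be lost; the documents do not support that. Loss follows only if the Section III sentence governs, and nothing says that it does or does not. What remains is the contradiction, and the database route is not explicit either: it does not say whether that database is central or on the phone.

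A reader might also take the exception in Section II.C as confirming an in-person rule. It does not, because it removes usage from all the listed routes, including administration by a tester at a community venue. It fits passive capture.

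A third tempting inference is that attenders are the more engaged, so losing remote participants inflates usage. Section II.B links remote contact to residence and feasibility, not to engagement. If assessment mode is unrelated to assigned feature, losing these people costs precision and need not bias the randomised comparison. The engagement argument is plausible for dropouts, but there it concerns the overall mean. The feature contrast is distorted only if the dropout rate, or the usage gap between dropouts and completers, differs by feature in a way that does not cancel, and the documents give no evidence of that.

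Finally, power is a weak measure of harm in a plan that treats significance testing as one source of information among several. That is fair, which is why the standard-error multiplier is shown beside it.

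**Conclusion.** The point holds as an unreconciled contradiction with a conditional consequence. Sections III and IV.A.2 give different retrieval routes for usage, and the Section III route cannot be carried out for participants assessed entirely remotely or for dropouts who miss the final session. If it is followed, the feature comparison loses precision in proportion to the remote share, and mean usage is probably overstated through the loss of dropouts.

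The sizes are illustrative. They rest on assumed remote shares and opening rates and on design values set for another outcome. The existence of the two routes, and the absence of a rule for remote and withdrawn participants, rest on the text alone. Daily steps and their power are unaffected, since the monitor can be mailed or hand-delivered.

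**What to change.** Replace the Section III sentence with the Section IV.A.2 route. Export usage logs from the app database for all 100 randomised participants over the four months from activation, whatever the assessment mode or completion status. Base the usage summaries and feature comparisons on all randomised participants, using recorded openings, including those logged before and after withdrawal from assessments where consent allows. Recorded openings avoid having to count every day after dropout as unopened, which is a debatable choice because a person may leave the assessments and keep using the app.

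Leave the Section II.C exception as it is. Removing it would make usage a measure to be mailed, emailed or administered.

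The cost is mainly protocol and SAP wording. If some logs are held only on the phone, one remote export step is needed for those users. The change should be made before any such logs become unrecoverable.
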